  - a. Aim 1. Test the translation of RDAD and IDEA programs designed to increase physical activities of older adult care receivers (CRs) with AD/RD and their CPs. Aim 2. Evaluate the short- and long-term effect of RDAD and IDEA on primary (*physical activity for CRs*) and secondary outcomes (*memory-related behavioral disturbances, physical functioning, and QOL for CRs; depressive symptomatology; perceived stress for CRs*). Aim 3. Test the moderating roles of CR-CP characteristics and severity of CR AD/RD on the treatment effect of RDAD and IDEA.
  - b. Study design: This study will utilize a 2-group randomized, single blind with staggered multiple baseline design and three follow-up assessments.

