- b. Pre-Treatment (baseline) assessment: Pre-treatment (baseline) assessments #1 and #2: Upon the random assignment, a research coordinator will contact subjects and schedule two pre-treatment assessments with a 6-week interval via telephone. CP will complete a 40 to 60-minute questionnaire via telephone for each assessment.
- c. Interventions: RDAD and IDEA are 9 1-hour sessions, conducted over 6 weeks in the participants' homes or a place of their choice where privacy is ensured. The sessions will be conducted twice a week for the first three weeks; once a week for the next three weeks; in the 12-week maintenance phase 4 15- minute follow-up phone calls will occur once a month for the next 4 months.

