address pre-stamped and addressed postcards will be given to all participants to be used to notify project staff for change of address and contact information.

5. Outcome Measures:

- a. Change in physical activity (CR) [Time Frame: Baseline (pre-treatment) to 13, 30, and 52 weeks post-treatment]
  - i. Measured by the number of days of exercise for at least 30 minutes in the past week. Higher scores indicate more days of activity.
- b. Change in physical functioning (CR) [Time Frame: Baseline (pre-treatment) to 13, 30, and 52 weeks post-treatment]
  - i. Assessed using mean score on physical functioning subscale of SF-36 (Medical Outcomes Study [MOS] 36-Item Short Form), consisting of 10 items assessing if participants' health limit them in activities such as walking, climbing, lifting, etc. on a 3-point scale ranging from 'yes, limited a lot' to 'no, not limited at all.' Higher scores indicate higher physical functioning.
- c. QOL (CR) [Time Frame: Baseline (pre-treatment) to 13, 30, and 52 weeks post-treatment]
  - i. Quality of life was evaluated using summed scores on the Quality of Life in Alzheimer's Disease (QOL-AD), a 13-item measure widely for quality of life in interventions with persons with AD/RD. Range of scores 13-52 with higher scores indicating better quality of life.
- d. Memory-related behavioral disturbances (CR) [Time Frame: Baseline (pre-treatment) to 13, 30, and 52 weeks post-treatment]
  - i. Assessed using mean scores on the memory-related subscale (7 items) of the 24-item Revised Memory and Behavior Problem Checklist (RMBPC). Higher scores indicate higher memory-related behavioral disturbances.
- a. Depressive symptomology (CP) [Time Frame: Baseline (pre-treatment) to 13, 30, and 52 weeks post-treatment]
  - ii. Depressive symptomology was assessed by summed score on the 10-item Center for Epidemiological Studies-Depression Scale (CESD-10), validated among older adults and commonly used with caregiver populations. Range of scores 0-27 with higher scores indicating higher levels of depression.
- b. Perceived stress (CP) [Time Frame: Baseline (pre-treatment) to 13, 30, and 52 weeks post-treatment]
  - iii. Assessed with mean scores on the Perceived Stress Scale (PSS) is a 14-item self-report measure designed to measure nonspecific, appraised stress during the past month. Higher scores indicate more stress.

6. Identifiability of data:

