exception being incidents of abuse of a dependent adult or minor child and risks of imminent harm to others or to the subject. All researchers have completed training in research with human subjects.

10. Analysis Plan: All participant data will be included in the study, according to the intent-to-treat principle, after excluding participants who withdrew prior to completing their baseline assessment. Analysis will be completed using Stata/MP 16.1 (StataCorp, 2019). To assess whether randomization of patients was successful, the two treatment groups will be compared by baseline demographics and clinical characteristics using two-sample *t*-tests, Chi-Square tests of independence, or Fisher's exact tests as appropriate. To test efficacy of the interventions, we will use linear mixed models to test the short- and long-term intervention effects on outcomes, with time treated as a categorical variable. The models included random intercepts and slopes for each participant to account for individual variability at baseline and change over time of the outcome variables and included baseline scores of the outcomes as fixed effects. Mixed-effects logistic regression models were estimated for binary outcomes, and continuous outcomes were estimated with mixed-effects linear regression models. Moderation effects were evaluated using interaction terms in the linear mixed models. The proposed sample size with a two-sided significance of 5% and a statistical power of 80% is sufficient to detect a small effect ( $d= 0.25$ ), which is greater than a minimal clinically important difference level. The statistical significance of all hypothesis tests were set at two-sided level of  $p = .05$ .

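### The plan names no deciding visit or testing rule for the IDEA-RDAD comparison on the primary outcome; if either of two or any of three tests may count, two-sided error is about 8-13% at assumed correlations of 0.8-0.5, not 5%

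*Combined protocol and SAP*

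**What the plan says.** Section 1, Aim 2, names care-receiver physical activity as the only primary outcome. It states the aim as "Evaluate the short- and long-term effect of RDAD and IDEA on primary" and secondary outcomes, without saying which comparison carries the claim. The design line in the same section describes a "2-group randomized, single blind with staggered multiple baseline design and three follow-up assessments".

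Section 4.e places the follow-ups after the in-person sessions (post #1), after the phone sessions (post #2) and at the 13th month. Section 5.a defines the outcome as "Change in physical activity (CR) [Time Frame: Baseline (pre-treatment) to 13, 30, and 52 weeks post-treatment" and gives none of the three time points priority.

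Section 10 is the whole analysis plan. It uses linear mixed models "to test the short- and long-term intervention effects on outcomes, with time treated as a categorical variable". It sets the level once for everything: "The statistical significance of all hypothesis tests were set at two-sided level of" 0.05. Interaction terms are mentioned only for moderation. The sample-size sentence claims that "The proposed sample size with a two-sided significance of 5% and a statistical power of 80% is sufficient to detect a small effect" of d = 0.25, but ties that effect to no visit or contrast.

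**The concern.** With time categorical, the model yields a separate estimate of the arm difference at each follow-up. Short- and long-term effects are both to be tested, each at the full 0.05, and nothing says which result decides the primary outcome. The deciding test could therefore be picked after the results are seen, and a reader of the report could not tell the planned test from the most favourable of several. Under that freedom, the 5% in Section 10 describes each single test, not the primary claim.

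The wording allows three testing structures: one joint test over the visits, which holds 5%; two tests, short-term and long-term, which is the most literal reading; or three tests, one per visit.

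**Working it through.** **Inputs from the documents.** Two-sided 0.05 for every test (Section 10); three follow-ups (Sections 4.e and 5.a); short- and long-term effects both tested (Aim 2, Section 10); 75 dyads per arm (Section 2.d); 80% power and d = 0.25 (Section 10).

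**Assumed.** The correlation r between the between-arm test statistics is not given, so it is varied. Section 10 fits participant random intercepts, so r = 0 is a ceiling on the error, not an expected value. Baseline adjustment lowers the correlation between visit contrasts below that between raw scores. With equal correlation 0.5 among baseline and follow-ups and one baseline covariate, it is (0.5 - 0.25)/(1 - 0.25) = 0.33. A row for 0.3 is therefore included.

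**Step 1: the plan's 5%.** One pre-specified test with |z| > 1.96 has error 5% under no effect. So has one joint test.

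**Step 2: any of k tests counts.** For independent tests the error is 1 - 0.95^k: 1 - 0.9025 = 9.75% for k = 2, and 1 - 0.8574 = 14.26% for k = 3. For equal correlation r, it is 1 minus the integral over x of φ(x)·[Φ((1.96 - √r·x)/√(1 - r)) - Φ((-1.96 - √r·x)/√(1 - r))]^k. Numerical integration gives:

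| r | either of two tests | any of three visits |
|---|---|---|
| 0 | 9.8% | 14.3% |
| 0.3 | 9.5% | 13.6% |
| 0.5 | 9.1% | 12.5% |
| 0.8 | 7.8% | 9.8% |
| 0.9 | 7.0% | 8.4% |

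At r = 0.8 to 0.5 the error is thus 7.8/5 = 1.6 to 12.5/5 = 2.5 times the stated level. Counting only results that favour IDEA, the error over the same range is 3.9-4.5% (two tests) and 4.9-6.3% (three), against 2.5%.

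**Step 3: with Holm over three visits.** The smallest p-value is compared with 0.05/3 = 0.0167, the next with 0.025 and the last with 0.05. Simulation with 1,000,000 draws gives an error of about 4.5% at r = 0.5 and 3.5% at r = 0.8, so the rule stays within 5%.

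**Step 4: what Holm costs in power.** Two starting points are used for a single visit: the plan's 80% (mean z = 1.96 + 0.84 = 2.80), and a plain two-sample test, with mean z = 0.25 × √(75/2) = 1.53 and power of about 33%. For r = 0.3 to 0.8:

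| Effect pattern | from 80% | from 33% |
|---|---|---|
| equal at all three visits, power per visit | 72-74% | 22-23% |
| none, half, full at visits 1, 2, 3; power at visit 3 | about 66% | about 20% |

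**The case against.** The strongest reply is that Section 10 sets a level per test and never says that any one significant visit makes the trial positive. Short- and long-term effects could be two separate claims, each entitled to its own 5%, and whether two claims on one outcome need joint control is partly a matter of judgement. This stands. A reader might infer that the trial's error rate simply is 8-14%. The documents do not support that, because the figure applies only if a success rule is used that the plan does not state. The 14% end also needs uncorrelated visits, which is implausible for repeated measures on the same people.

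A second tempting inference is that the trial will be judged on change within each arm. Some wording leaves room for this: "To test efficacy of the interventions" is plural, and Section 4.b has staff "schedule two pre-treatment assessments with a 6-week interval via telephone". But the two-group randomisation, the baseline comparison of the arms and the equal exposure designed into both programmes (Section 4.c.ii) all point to IDEA against RDAD. The within-arm reading is not excluded, but it is the less supported one, so no error rate is built on it here. One sentence in the plan would close it off.

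It might also be said that a standard group-by-time test already holds 5%. It does, but the plan does not specify one. Section 10 enters baseline scores as fixed effects. If only the follow-ups are then modelled as outcomes, the interaction alone asks whether the arm difference varies between visits, and it could miss a constant benefit.

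**Conclusion.** The gap is real and should be closed: the single primary outcome can be claimed from any of several unadjusted tests, and no section rules this out. Conditional on either of two between-arm tests counting, two-sided error is about 8-9%; conditional on any of three visits counting, about 10-13%. Both ranges assume correlations of 0.8-0.5 and no true difference at any visit. Lower correlations raise them to at most 9.8% and 14.3%.

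What is established is under-specification with a quantified possible consequence, not a demonstrated error rate. Whether the stated 80% power can be reached with 75 dyads per arm is a separate question; the 33% figure serves here only as a second starting point for the cost of the fix.

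**What to change.** In Section 10, state that the primary contrast is the between-arm IDEA-RDAD difference in care-receiver physical activity and that within-arm change is descriptive. Then declare one rule that holds 5% overall. Suitable wording would be: *The IDEA-RDAD difference will be tested at post #1, post #2 and the 13th-month follow-up, with Holm's procedure at an overall two-sided 0.05. All three estimates will be reported with confidence intervals whatever the outcome of the tests.*

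Holm keeps both short- and long-term claims available. Alternatives are:

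- **One joint test.** If baseline is a covariate, it must test group and group-by-time together, not the interaction alone.
- **A fixed sequence.** Its cost depends on the order. Testing the 13th month first leaves power there untouched; testing post #1 first puts a late effect at risk.

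Some wording in Section 10 is in the past tense. If results have already been examined, label the rule as set afterwards.

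The change needs no new data or visits. Its price is the loss of power shown in the working: with Holm and an equal effect at all visits, about 6-8 points per visit from 80%, or about 10-11 points from 33%.
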